9.3 Safety Oversight (ISM plus DSMB)

9.3.1 Independent Safety Monitor (ISM)

The ISM is a physician with relevant expertise whose primary responsibility is to provide independent safety monitoring in a timely fashion. The ISM will review SAEs and other AEs as needed and provide an independent assessment to DMID. UVA will have an ISM with experience in infectious diseases or internal medicine.

9.3.2 Data and Safety Monitoring Board (DSMB)

This clinical trial will utilize a DSMB, which will be comprised of an independent group of experts with experience with early phase clinical research studies. The primary responsibility of the DSMB is to monitor subject safety. The DSMB is external to DMID and composed of at least three voting members. The DSMB will consist of members with appropriate expertise to contribute to the interpretation of the data from this trial. Committee activities will be delineated in a DSMB charter that will delineate membership, responsibilities, and the scope and frequency of data reviews. The DSMB will operate on a conflict-free basis independently of the study team. DMID, the DSMB, the ISM or the PI may convene ad hoc meetings of the DSMB according to protocol criteria or if there are concerns that arise during the study. The DSMB will have access to unblinded data during its closed session, if applicable. After its assessment, the DSMB will recommend continuation, modification, or termination of the clinical trial.

The DSMB will conduct a review of all available safety data after each cohort has completed the day 8 study visit (7 days following the first study inoculation). The review will also include all available safety data on second inoculations accrued through the time of data freeze for the DSMB meeting and the DSMB will recommend continued enrollment of the remaining subjects, modification, or discontinuation of enrollment.

If any of the halting rules are met following the first or second study challenge, the study will not proceed with the remaining enrollment or study challenge without a review by and recommendation from the DSMB to proceed.

Upon completion of this review and receipt of the advice of the DSMB, DMID will determine if study entry or study dosing should be interrupted, or if study entry and study dosing may continue according to the protocol.

A final review of Safety data will be conducted after the study is completed. This review may be performed electronically if the DSMB Chair agrees.

9.3.3 Safety Monitoring

This study is not blinded and involves an intervention that is well-characterized and has an extensive safety record. The investigational material for this study is the challenge pools that will be used for the RV infections. The previous studies that have been done with these pools, as well as the extensive experience with the RV challenge model, in general, mitigate concern about the safety of the model.

Safety will be monitored during the challenge studies by the PI. Results of the challenge studies and collection of AEs will be reviewed by the DSMB as described above.

10 CLINICAL MONITORING

10.1 Site Monitoring Plan

Under the U01 mechanism, site monitoring is the responsibility of the investigators. To ensure that human subject protection, study procedures, laboratory procedures, study intervention administration, and data collection processes are of high quality and meet sponsor, CGP/ICH, and regulatory guidelines, and that the study is conducted in accordance with the protocol and sponsor SOPs, and protocol specific MOP, the study will be monitored by an external, independent entity, the UVA School of Medicine Clinical Trials Office (<https://research.med.virginia.edu/clinicalresearch/research-resources/offices-supporting-clinical-research/clinical-trials-office/available-services/>).

In brief, site visits will be made at standard intervals as defined by the Site Monitoring Plan. Monitoring visits will include, but are not limited to, review of regulatory files, accountability records, case report forms, informed consent forms, medical and laboratory reports, and protocol and GCP compliance. Study monitors will meet with investigators to discuss any problems and actions to be taken and document visit findings and discussions. See detailed protocol monitoring plan for details. The details of the site monitoring process for this study are given in a separate document (Protocol Monitoring Plan). This Monitoring process is separate and independent from the internal Quality Management Process to be conducted by the PI as described in Section 12 of this protocol.

11 STATISTICAL CONSIDERATIONS

11.1 Study Hypotheses

The overall hypothesis that will be addressed by this proposal is that Th and Tfh cells directed against conserved RV epitopes expand upon RV exposure and some of these cells persist as stable cross-reactive memory populations capable of displaying lineage-specific protective functions upon re-infection with related or unrelated strains of RV. The IP is not the object of this study and there are no hypotheses related to the study product.

11.2 Study Outcome Measures

This study is a mechanistic study, and thus, the conventional framework of primary and secondary outcome measures used in standard clinical trials does not apply.

11.2.1 Primary Objectives

To assess the relationship between T-cell immunity induced by infection with the rhinovirus serotype RV-16, and the host response to homologous infection with RV-16 or the host response to heterologous infection with RV-39.

11.2.2 Exploratory Objectives

The major objective of the study is to perform mechanistic studies that apply state-of-the art experimental technologies to identify, enumerate, and monitor a broad array of known and novel cell types during challenge with RV-16 and re-challenge with RV-16 or RV-39 in order to identify hallmarks of cross-protection. The technologies applied include, but are not limited to, MHCII tetramer staining, mass cytometry, and single-cell gene expression profiling. Owing to the large amounts of data that will be generated and the exploratory nature of the study, outcomes cannot be predicted. Exploratory objectives include, but are not limited to, the following: (1) Identify new molecular signatures of RV-specific T cells. (2) Evaluate the quality and quantity of T-cell responses. (3) Identify, enumerate and monitor a broad array of immune cell types (e.g., B-cell populations, CD8+ T-cells, gamma delta T-cells, NKT cells, etc.), and novel cell types. (4) Test multiple relationships between immune cell parameters and infection, serum antibodies, and symptoms (illness), at each sampling time point during RV challenge and re-challenge.

11.2.3 Primary Outcome Measure

Correlation between the number of pre-existing RV-16-specific T cells at Week 15, and infection after homologous re-challenge with RV-16 or infection after heterologous re-challenge with RV-39 at Week 15. With regard to measurement transformation, in our past characterization of T-cell responses to RV-16 and RV-39, we have found that the measurement distribution of many of the aforementioned outcome measures (e.g., T-cell response, viral load) exhibit prominent right-tailed skewness, which depending upon whether a parametric or a non-parametric analysis approach is utilized to analyze the data, has required either rescaling the outcome data to a logarithmic scale (e.g., log₁₀ scale), or rescaling the data to a rank scale, respectively.

11.3 Sample Size Considerations

11.3.1 Sample Size Calculation Summary

The number of subjects enrolled for initial challenge with RV16 (80) is determined based on power analyses related to the primary outcome measure in Aim 2. In Aim 2, our sample size is designed to address the hypothesis that ***high frequencies of pre-existing RV-16-specific memory T cells directed against conserved epitopes protect against RV-39 infection.*** **Our primary objective is to test the relationship between the frequency of RV-16-specific memory T cells at 15 weeks and viral infection in response to re-challenge with RV-16 or RV-39.** In order to do this, we must first establish that there is a scientifically meaningful reduction in the RV infection rate for secondary versus primary RV challenge. A sample size of 35 volunteers per re-challenge will provide a two-sample test of equal proportions with 85% statistical power (with a one-sided $\alpha=0.025$ type I error rate) to detect a reduction of as small as 28% between the infection rate following primary challenge and the infection rate following secondary challenges.

If we have 35 volunteers per re-challenge, and if the underlying bivariate correlation between the frequency of RV-16-specific memory T cells at 15 weeks and viral infection in response to secondary challenge with RV-16 or RV-39 is at least 0.46 units in absolute magnitude - which if true, would be considered a scientifically meaningful association - we expect to have at least 0.80 statistical power to reject the null hypothesis that there is no correlation between the frequency of RV-16-specific memory T cells at 15 weeks and viral infection in response to secondary challenge with RV-16 or RV-39.

11.3.2 Power Calculation Details

The “TWO SAMPLE FREQ” statement of the SAS version 9.4 (SAS Institute Inc., Cary, NC) “POWER Procedure” was used to conduct the first portion of the power analysis. As user input, the infection rates for the primary and secondary RV challenges were specified as 0.90 and 0.65, respectively. A zero difference in the infection rates of the primary and secondary RV challenges was specified as the null difference and the alternative difference was specified as a 0.25 unit reduction (i.e., $0.90 - 0.65$) in the secondary RV challenge infection rate compared to the primary challenge infection rate. In accordance with the alternative hypothesis “less than” direction, an $\alpha=0.025$ one-sided type I error rate was specified, and the group sample sizes were specified as $n=80$ for the primary RV challenge and $n=35$ for the secondary RV challenge. Based on this set of input parameters, a sample size of 35 volunteers per re-challenge should provide a statistical test with at least 85% power (with a one-sided $\alpha=0.025$ type I error rate) to detect a reduction of as small as 28% (i.e., $[(0.90-0.65)/0.90 \times 100\%]$) between the infection rate following primary challenge and the infection rate following secondary challenge.

The “ONE CORR” statement of the SAS version 9.4 “POWER PROCEDURE” was used to conduct the second portion of the power analysis. As user input, the null correlation was specified to be zero and the alternative correlation was specified to be 0.46. The test statistic was specified as the “Fishers z statistic”, and the two-sided type I error rate (α) was specified as $\alpha=0.05$. Based on this set of input variables, the power to detect a correlation of 0.46 in absolute magnitude is 0.81.

The rationale for the number of subjects screened is as follows:

- 750 volunteers will be screened for antibody to provide approximately 120 volunteers who are seronegative to both RV-16 and RV-39.
- Of the 120 resulting seronegative volunteers, approximately 96 will have a matched RV tetramer available for the T-cell studies.
- 80 eligible subjects (after review of other inclusion/exclusion criteria) will be challenged with RV-16, approximately 72 (90%) will be infected.
- 70 subjects (35 per virus) will be rechallenged with either RV-16 or RV-39.

Note that volunteers who have a positive respiratory virus panel (PCR for respiratory syncytial virus [RSV], influenza, parainfluenza, metapneumovirus, rhino/enterovirus, and adenovirus) from nasal lavage on the day of RV challenge, or who shed a RV other than the challenge virus in nasal lavage over the course of the study, will be excluded from the analysis.

Owing to the powerful, yet exploratory, nature of mass cytometry experiments, we anticipate that a much smaller sample size will be necessary to discover novel cell types induced by RV exposure that are biologically relevant. Our proposed work is at the forefront of science in this regard. As an example, recent work describing longitudinal monitoring of Tfh cells during HIV infection in a primate model using mass cytometry was published in *Science Translational Medicine* with a sample size of 8 [36].

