The current study will use major histocompatibility complex class II (MHCII) tetramers that display conserved RV-16 peptide epitopes to identify and track circulating RV-specific CD4⁺ T cells in subjects who receive sequential RV challenges with RV-16 and RV-39 (Fig. 1 and Table I). This will allow us to interrogate adaptive immunity to heterotypic RV strains. Preliminary work performed under a separate pilot study established the feasibility of this approach. In that study, tetramer-guided epitope mapping [16] was used to develop two DRB1*0401 tetramers that displayed conserved RV-39 epitopes (one each for capsid protein VP1 and VP2). The pilot study included 16 healthy DRB1*0401+ subjects (ages 18-60 years old) who participated in a RV-39 experimental challenge study. All subjects had no history of allergies and were seronegative for RV-39 (serum neutralizing antibody titer $\leq 1:4$) (see enrollment, Fig. 2). Challenge with RV-39 was administered intranasally (2 doses per nostril of a 0.25 mL solution containing 100 TCID₅₀/mL). RV-39 antibody titer was re-tested immediately before challenge (day 0) and during convalescence (day 21). Those subjects experiencing ≥ 4 -fold increase in RV-39 serum neutralizing antibody titer, or at least one RV-39 positive nasal culture, were considered infected. Peripheral blood mononuclear cell (PBMCs) were isolated from DRB1*0401+ subjects before RV challenge (days -28 and 0), and during acute (day 5) and convalescent (day 21) phases (model, Fig. 2). Samples were frozen and then thawed for analysis upon study completion. Tetramer staining and flow cytometry analysis was performed using established methods. A control tetramer containing an irrelevant peptide (GAD555-567) provided a negative control [23-25, 27, 28].

[figure not shown]
[figure not shown]

Fig. 2. Experimental RV-39 challenge study. Enrollment of DRB1*0401+ subjects and RV-39 challenge study design. Arrows in the model denote PBMC sampling time points.

Of the 16 DRB1*0401+ subjects enrolled, 12 were infected and 4 were uninfected. In *post hoc* tests, 3 subjects had evidence of recent RV exposure based on positive serum neutralizing

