7.4 Second Virus Challenge**7.4.1 Study day RC0 (study visit RC 1)**

- Baseline symptom assessment
- Review of interval medical history
- Urine pregnancy screen for females who are not surgically sterile or post-menopausal
- Review of AEs
- Review of concomitant medications
- Nasal lavage for respiratory virus PCR, and cytokines
- Challenge with RV

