8.3 Laboratory Evaluations

8.3.1 Virology

Detection of virus in the Study day 0 nasal lavage is done by a multiplex PCR (Luminex xTAG[®] Respiratory Viral Panel [Austin, TX]) in the Clinical Laboratory of the UVA Medical Center.

RV cultures will be done by routine methods [33]. Nasal lavage collected on Study days 1-5 are cultured for RV by inoculation into two tubes of human embryonic lung fibroblast cells (either MRC-5 or WI-38) and incubation on roller drums at 33 °C for 14 days. RV is identified by the development of typical cytopathic effect. One isolate from each subject who sheds virus is confirmed as the challenge RV serotype by a neutralization assay with HRV type 39 or type 16 antiserum. Subjects who have at least one positive culture for the challenge virus or who have at least a four-fold rise in antibody titer to RV type 39 are considered infected. Previous studies have established that the challenge inoculum is not re-isolated from uninfected volunteers, thus a single positive culture is evidence of virus replication in the upper respiratory tract [34]. Serial 10-fold dilutions of the nasal lavage will be cultured in microtiter plates for semi-quantitative determination of viral shedding. Titers are calculated using the method of Karber.

We will use a qPCR assay that has been previously described by other members of our research group [35]. Briefly, RNA is extracted using QIAamp RNA isolation kits (Qiagen, Crawley, UK) and cDNA is generated. The cDNA is amplified using primers and probes specific for conserved regions of RV and detected by qPCR (RV forward 5'-GGCCCTGAATGTGGCTAA-3'; RV reverse 5'-ATCCCCGCAATTGCTCGTTAC-3'; probe 5'-FAM/ CTTGCAGCCAATGCA-BHQ-3') (Integrated DNA Technologies, Coralville, IA). Virus quantity is determined by comparison to a standard curve.

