11.5 Analysis Plan

11.5.1 General Statistical Plan

General statistical support related to the primary outcome measure, and many of the parameters assessed under exploratory objectives will be provided by [name], MS (Pstat® Accredited Senior Biostatistician, Department of Public Health Sciences). Analyses performed by [name] will include, but are not limited to: (a) comparing infection rates resulting from primary challenge with RV-16 and re-challenge with RV-16 or RV-39, (b)

comparing RV-specific T-cell numbers before and after primary RV-16 challenge, (c) examining correlations between specific T-cell numbers and quantitative shedding as assessed by culture and qPCR as well as the time to virus shedding, (d) comparing clinical outcomes (e.g., cytokine response, and symptom scores) between primary RV challenge and RV re-challenge, and (e) examining correlations between RV specific T-cell numbers and clinical outcomes.

11.5.2 Primary Outcome Analyses (Correlation between the number of pre-existing RV-16 specific T-cells (15 wks.) and infection following re-challenge with RV-39 as assessed by virus shedding in nasal lavage)

Infection rates at primary challenge and the infection rates at secondary challenge will be analyzed by way of a binomial generalized estimating equation (GEE) model [37]. The GEE model response variable will be a binary indicator variable that will be assigned the value 1 if the volunteer is deemed infected on RV challenge and the value 0 will be assigned otherwise. The GEE model predictor variable will be 3 level classification variable. One level will differentiate the primary RV-16 challenge outcome data from the secondary RV challenge outcome data, a second level will identify the secondary RV-16 challenge outcome data, and the third level will identify the secondary RV-39 challenge outcome data. Since we expect that approximately 90% of the volunteers who undergo the primary RV-16 challenge will be eligible to undergo either RV-16 or RV-39 re-challenge, we cannot legitimately assume that the primary challenge infection status and re-challenge infection status of the volunteers who undergo re-challenge are statistically independent. To account for possible *intra-subject* measurement correlation, the components of the GEE model variance and covariance matrix will be estimated by the Huber and White sandwich estimator [38, 39].

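### The analysis exclusion in section 11.3.2 is worded by volunteer, so a stray virus at re-challenge also removes first-challenge data that it cannot have affected

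*Combined protocol and SAP*

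**What the plan says.** The only rule for excluding data from analysis is a note at the end of section 11.3.2. It has two parts.

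- **Panel part.** It begins "Note that volunteers who have a positive respiratory virus panel" and fixes the time as "from nasal lavage on the day of RV challenge". It does not say which challenge.
- **Shedding part.** It covers those "who shed a RV other than the challenge virus in nasal lavage over the course of the study, will be excluded from the analysis".

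Both parts take the volunteer as their subject and have the same consequence. The analysis in question is not specified, and no analysis set is defined elsewhere.

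Either challenge can trigger the rule. Sections 7.3.1 (Day 0) and 7.4.1 (RC Day 0) both list "Nasal lavage for respiratory virus PCR, and cytokines". Sections 7.3.2 and 7.4.2 schedule daily RV culture on the five days after each challenge. Section 8.3.1 says how a non-challenge rhinovirus would be recognised: "One isolate from each subject who sheds virus is confirmed as the challenge RV serotype by a neutralization assay".

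The infection-rate model in section 11.5.2 works by challenge record: "The GEE model predictor variable will be 3 level classification variable", with levels for primary RV-16, secondary RV-16 and secondary RV-39. The same section expects that "approximately 90% of the volunteers who undergo the primary RV-16 challenge will be eligible" for re-challenge, so some volunteers enter with a first-challenge record alone.

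**The concern.** A virus picked up around Week 15 cannot have changed whether the volunteer was infected, shed virus or had symptoms in the five days after the first challenge, or how T cells had expanded by Day 7 and Day 28. Yet a literal reading of the shedding part, and one fair reading of the panel part, removes all of those data.

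The filter is also uneven. A volunteer who never reaches re-challenge cannot fail it there and keeps the first-challenge record. One who is re-challenged and happens to carry a wild virus loses it.

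The analyses touched are the primary-versus-re-challenge infection comparison (11.5.2), and the pre/post T-cell and antibody models and the Day 0-5 viral-load, cytokine and symptom models (11.5.3). At stake are valid observations in a small study, and a first-challenge data set that depends on a later event for no analytical reason.

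**Working it through.** **Inputs from the documents.** 80 volunteers at first challenge, 70 re-challenged (35 per virus), infection rates 0.90 and 0.65, alternative correlation 0.46, two-sided 0.05, stated power 0.81 (all 11.3.2).

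**Assumed inputs.** The probability p that a challenge triggers the exclusion is not given. I use 5%, 10% and 15%, the same at each challenge and independent between them.

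**The plan's own figure.** Fisher z power for r = 0.46 at n = 35, with the r/(2(n-1)) bias term, is 0.814 (0.803 without the term). The stated 0.81 reproduces. It assumes 35 analysable volunteers per virus, that is, no exclusions.

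**First-challenge records kept.**

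- Exclusion by challenge: 80(1-p).
- Exclusion by volunteer: 80(1-p) - 70(1-p)p. The second term counts volunteers with a clean first challenge who are re-challenged and then trigger the rule.
- Relative interval width: the square root of the ratio of the two counts.

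| p | By volunteer | By challenge | Records recovered | Width ratio |
|---|---|---|---|---|
| 5% | 76.0 - 70×0.95×0.05 = 72.7 | 76.0 | 3.3 | √(76.0/72.7) = 1.02 |
| 10% | 72.0 - 70×0.90×0.10 = 65.7 | 72.0 | 6.3 | √(72.0/65.7) = 1.05 |
| 15% | 68.0 - 70×0.85×0.15 = 59.1 | 68.0 | 8.9 | √(68.0/59.1) = 1.07 |

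**Primary correlation.** It uses only the Week 15 T-cell count and re-challenge infection. If a first-challenge hit continues to remove both records, the number per virus is 35(1-p)² whether or not the re-challenge part of the rule is reworded: 31.6, 28.4 and 25.3. The rewording changes nothing here.

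**Primary-versus-re-challenge comparison.** The smaller re-challenge group dominates the variance. Using the plan's independent two-sample approximation at p = 10%:

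- by challenge: 0.09/72.0 + 0.2275/28.35 = 0.00927
- by volunteer: 0.09/65.7 + 0.2275/28.35 = 0.00939

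The standard error ratio is √(0.00939/0.00927) = 1.006, so the recovered records tighten this comparison by under 1%. The benefit falls on the analyses of the first challenge itself.

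**The case against.** **The rule may have been meant per challenge.** The panel part refers to a single challenge day, and the analysis it mentions is undefined, so a per-challenge reading is available. This stands for the panel part, where the point is that the text leaves the unit open. It does not stand for the shedding part, whose window is the whole study.

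**A reader might infer lost power for the primary correlation.** The documents do not support this. The proposed change leaves the re-challenge numbers alone, and section 5.1 lets cohort size vary in years 2 and 3 so that the required number is available for analysis. Section 4.2 also resizes the final cohort to reach about 70 re-challenged, although for attrition only.

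**A reader might infer biased first-challenge results.** Selecting on a later event is untidy. But if a stray virus at Week 15 is unrelated to the first-challenge outcome, it costs numbers and does not shift the estimate. The documents show no link between the two.

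**A reader might say that a non-rhinovirus hit on Day 0 should not remove the re-challenge pair.** That is a judgement. The primary objective concerns T-cell immunity induced by RV-16 infection, and a first challenge given with another virus present may not represent it. Excluding both records in that case is defensible.

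**The rates have no source.** This is correct. In the pilot (background section), "3 subjects had evidence of recent RV exposure based on positive serum neutralizing" antibody or PCR on day 0. That 3 of 16 (19%) is not a panel-positivity rate: it mixes serology with PCR, concerns rhinovirus exposure only, and used a titre cutoff of 1:4 against 1:2 here. Section 5.3.2 also bars volunteers with an upper respiratory infection in the two weeks before challenge, which should lower the rate.

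**Conclusion.** The point holds for hits at re-challenge. As worded, section 11.3.2 discards first-challenge data that a virus found about 15 weeks later cannot have affected, and no planned model requires it. The reading is plain for non-challenge rhinovirus shedding and arguable for the RC Day 0 panel.

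The size is modest: about 3, 6 or 9 first-challenge records recovered at assumed trigger rates of 5%, 10% or 15% per challenge. These figures rest on the assumed rates, on independence between challenges, and on 80 and 70 volunteers reaching the two challenges. Neither a power loss for the primary test nor bias is established. The case for acting is that valid data are kept at almost no cost and that the unit of exclusion is settled before infection outcomes are analysed in an unmasked study.

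**What to change.** Reword the note in section 11.3.2 to name the challenge to which each exclusion applies.

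- **Hit at re-challenge** (positive RC Day 0 panel, or a non-challenge rhinovirus on RC Days 1-5): remove the re-challenge record only and keep the first-challenge record. The Week 15 blood sample is both the last first-challenge specimen and the re-challenge baseline (Appendix A, footnote 1). State that for this rule it belongs to the re-challenge record, since a virus present on RC Day 0 could affect it.
- **Hit at first challenge:** the primary analysis may go on excluding both records. Retaining the re-challenge pair after a non-rhinovirus panel hit can be a sensitivity analysis.
- **Sensitivity analysis:** repeat the first-challenge analyses and the GEE with whole-volunteer exclusion.
- **Reporting:** give the number of exclusions by challenge and by reason.

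The cost is one paragraph of text and a small number of extra analysis runs. No sample, visit or change in recruitment is needed.
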